3.5.2.2. Dose Modifications for Non-Hematologic Toxicity for VCR, and dexamethasone

If the subject experiences any non-hematologic clinically significant Grade 3 or greater toxicity felt to "possibly" be related to any agent, hold the protocol therapy until it resolves to \leq Grade 2. If related to VCR, reduce the dose of VCR to by one dose level (per Table 3-1); if at lowest dose level, resuming treatment with VCR will be at Investigator's discretion after discussion with Sponsor. Refer to product label information for specific toxicity management. If related to dexamethasone, resuming treatment with dexamethasone will be at the discretion of the Investigators. If the toxicity recurs, subject will be removed from study. If protocol therapy is withheld for more than 2 weeks for toxicity possibly, probably, or definitely related to protocol-based therapy or up to 4 weeks for any other reason, subjects will be removed from protocol.

Subjects who have been dose-reduced cannot be returned to a higher dose level.

Toxicities in an individual subject must resolve to Grade 2 or to baseline levels before proceeding with the next cycle of treatment.

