Subjects will continue on their assigned dose level throughout all cycles and through maintenance. Intra-subject dose escalations are not permitted. Dose modifications are not permitted during the GS-9973 Lead-in or Cycle 1 as this is used to assess dose limiting toxicities (DLT). Following the completion of Cycle 1, if a GS-9973 related AE of Grade \geq 3 occurs, the subject will have GS-9973 held until the AE improves to Grade \leq 1 and then may resume study therapy at the prior dose (or decreased by 1 dose level after discussion with Sponsor). For subjects assigned to Dose Level 1, the decreased dose of GS-9973 will be defined as 100 mg orally twice daily.

Dose Escalation treatment schedule is outlined in the schema below:

Dose Expansion:

At the time of this amendment, there have been no DLTs in the Phase 1 portion of the study. However, due to the low response rate to ENTO + vincristine + dexamethasone in relapsed/refractory ALL patients, it has been decided not to proceed with the dose expansion (Phase 2) portion of this trial. Prior to this amendment, dose expansion had been initiated at 400 mg BID, but was subsequently closed with no subjects enrolled.

Maintenance:

	It is anticipated that most subjects who are transplant eligible will receive hematopoietic stem cell transplant (HSCT) or therapy with curative intent if a complete remission (CR) is reached. In the absence of a suitable alternative therapeutic option, subjects who obtain clinical benefit (at least partial response [PR]) after completing both cycles of induction therapy in dose escalation may continue GS-9973 at the assigned dose level during maintenance for up to 36 cycles. Subjects will continue GS-9973 and VCR at their assigned dose. GS-9973 will continue to be taken orally twice daily with VCR to be administered on Day 1 of each 28-day cycle and dexamethasone 20 mg total dose daily for 4 days (either 10 mg twice daily or 20 mg once daily) on Days 1-4 and Days 15-18 of each 28-day cycle. Bone marrow evaluations and additional central nervous system (CNS) directed therapy can be performed as clinically indicated during maintenance.
Number of Subjects Planned:	Approximately 30
Target Population:	Adult subjects with relapsed or refractory B-cell lineage ALL

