3.5.2. Guidelines for Dose Modifications

3.5.2.1. Dosing Delays/Dose Modifications Attributed to GS-9973 (beyond Cycle 1)

If the following signs or symptoms are medically manageable, they are not to be a consideration with respect to the subject's dosing or continuation on study: nausea/mild vomiting/diarrhea, drug-related fever or chills, transient and correctable laboratory test abnormalities, line associated thrombosis, or alopecia. See Appendix 3.

There will be no dose modifications during Lead-in or Cycle 1 for GS-9973, VCR, or dexamethasone. Subjects experiencing toxicity attributed to these agents during Cycle 1 requiring discontinuation of any drug shall be removed from study and will be considered a DLT.

Dose modification of GS-9973 in subsequent cycles is permitted following guidelines provided in Appendix 3. Subjects who experience a non-hematologic toxicity assessed as GS-9973 related that is Grade 3 or higher will hold dosing of GS-9973 until the toxicity resolves to \leq Grade 1, and then may resume study therapy at the prior dose through the end of the cycle (or decreased by 1 dose level after discussion with Sponsor). For subjects assigned to Dose Level 1, the decreased dose of GS-9973 will be defined as 100 mg orally twice daily. Missed doses are not to be made up.

Adverse events and laboratory abnormalities will be graded using the CTCAE, Version 4.03.

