 b Vital signs (includin least 5 minutes. c Following consent, Subjects should be specifically if there d Bone marrow aspiration of the specifical spe	adverse events contacted by pl are any AEs si	will be assessent none (or in personne stopping the	ed pre- son, if ne stud	and po necess y.	ost-dos ary) 3	e durii 0 days	ng eac (±7 d	h clin ays) a	ic visi fter th	t, and t e subje	30 (±7) ect's la) days st dos	follow e of stu	ing cor dy dru	npletic	on of t	he sub	ject's last dose	of study drug.
e CBC with different f For female subjects during Cycle 1 on I g Pharmacokinetic pe	of childbearin Day 1 (expansio pripheral blood	g potential, ser on). Pregnancy samples will b	um tes tests v e obtai	vill be ned pr	perfor e-dose	med or during	n a Da g Lea	iy 1 of d-in of	each Day	cycle 1 -7; Cy	hereaf	ter. n Day	1, 8, 2	8 and 0	Cycle	2 on D	ay 28.	PK blood sam	ples will also b
collected 1.5 hours independent of PK CSF samples will b	time point.			,			2					-	2		2			hylaxis admini	stration is
 k Subjects with EMD l Treatment with GS- m Vincristine will be a n Dexamethasone (20 dexamethasone (20 o CNS prophylaxis point 	-9973 will be c administered du) mg BID; dose mg QD or 10 r	ontinuous. GS uring Cycles 1 d for 4 days) w ng BID; dosed	-9973 and C will be for 4	should ycle 2 disper days) v	l be dis on Day used du vill be	spense ys 1, 8, uring C disper	d on I , 15, 2 Cycle	Day 28 2 and 1 on E	to ind during ay 8 a	g Mair nd Da	itenanc y 22 a	e on I nd dur	Day 1 o ring Cy	f each	cycle.	2		15. During Ma	ntenance,

Appendix 3.	Management of Clinical and Laboratory Adverse Events	

	Dosing Delays/Dose M	odifications for AEs Attributed to	GS-9973 (beyond Cycle 1)	
Adverse Event	Grade 1	Grade 2	Grade 3	Grade 4
Dermatological	Maintain current dose level and schedule.	Maintain current dose level and schedule.	Withhold dosing until ≤ Grade 1 or return to baseline. Resume dosing at current dose level. If re-challenge at current dose level results in recurrence, may resume dosing at same or lower dose level at investigator discretion.	Withhold dosing until Grade ≤1 or return to baseline. May resume at lower dose level or discontinue dosing at investigator discretion.

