Other Study Drug Related, Non hematological Adverse Events	Maintain current dose level and schedule	Maintain cu schedule	rrent dose level and Withhold dosing unti return to baseline. May resume dosing a lower dose level or di dosing at investigator		at initial or liscontinue	Withhold dosing until Grade ≤1 or return to baseline. May resume dosing at initial or lower dose level or discontinue dosing at investigator discretion	
	Dosing Delays/Dose Modificat	tions for Non	-hematologic AEs At	tributed to VCR (bey	ond Cycle 1)		
Grade 1	Grade 2		Grade 3		Grade 4		
Maintain current dose level and schedule	Consider withholding dose unt resolves to Grade ≤ 1 or basel. May resume dosing at same do (or dose-reduced by 50%)	ine.	Withhold dosing until AE resolves to Grade ≤ 1 or baseline. May resume dosing at same dose level of dose-reduced by 50%.		or baseline. May resume do discontinue per	ag until AE resolves to Grade ≤ 1 osing at 50% dose-reduction or r investigator discretion. ole neuropathy, consider permanent.	
D	osing Delays/Dose Modifications	for Non-hem	atologic AEs Attribu	ted to dexamethason	e (beyond Cycle	1)	
Grade 1	Grade 2		Grade 3		Grade 4		
Maintain current dose level and schedule	Consider withholding dose un resolves to Grade ≤ 1 or basel. May resume at same dose leve (or dose-reduced by 50%)	ine.	Consider withholdin resolves to Grade ≤ May resume dosing level/frequency or do	1 or baseline. at same dose	 Withhold dosing until AE resolves to Grade ≤ 1 or baseline. May resume dosing at 50% dose-reduction or discontinue per investigator discretion. For unacceptable myopathy, consider permanent discontinuation. 		

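### Protocol 3.5.2.2 and the Appendix 3 vincristine table give conflicting restart rules after a Grade 3 vincristine toxicity beyond Cycle 1, and nothing says which governs

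*Protocol*

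**What the plan says.** Protocol 3.5.2.2 covers non-hematologic toxicity for VCR and dexamethasone. When a clinically significant toxicity of Grade 3 or greater is possibly "related to any agent, hold the protocol therapy until it resolves to" Grade 2 or lower, therapy may restart. If VCR is the cause, the site must "reduce the dose of VCR to by one dose level (per Table 3-1"). At the lowest level, resuming VCR is left to the investigator after discussion with the Sponsor. Resuming dexamethasone is left to the investigators. A subject whose therapy is withheld for more than 2 weeks because of related toxicity leaves the protocol.

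The Appendix 3 table for non-hematologic events attributed to VCR beyond Cycle 1 says at Grade 3: "Withhold dosing until AE resolves to Grade ≤ 1 or baseline. May resume dosing at same dose level of dose-reduced by 50" percent. At Grade 4 it uses the same restart grade and offers a 50% reduction or discontinuation. At Grade 2 it says to consider withholding.

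The Appendix 3 dexamethasone table says to consider withholding at Grade 3 and to withhold at Grade 4, each until Grade 1 or lower or baseline. At Grade 4 it continues: "May resume dosing at 50% dose-reduction or discontinue per investigator discretion".

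Protocol 3.5.2.1 bars dose modification of all three drugs in Lead-in and Cycle 1, so 3.5.2.2 and Appendix 3 cover the same period of treatment.

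**The concern.** Two parts of one protocol give different instructions for the same drug, event and period. Take a subject with Grade 3 peripheral neuropathy, which Protocol 1.5.1 lists as a VCR side effect. A site working from 3.5.2.2 may restart VCR once the event is Grade 2, but must lower the dose. A site working from Appendix 3 must wait for Grade 1 or baseline, but may then give the full dose. Grade 2, where 3.5.2.2 allows a restart, is the grade at which Appendix 3 says to consider withholding.

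Each text is the more cautious on one element: Appendix 3 on timing, 3.5.2.2 on dose. A site that follows only one text can break the other. Subjects with the same toxicity could restart at different grades and doses depending on which page the site opened, in a study whose primary endpoint is safety.

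**Working it through.** There is no planned figure to reproduce. The check sets the texts side by side and applies each to the VCR doses in Protocol Table 3-1.

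**Inputs.** VCR per dose at Levels 1, 2, 3 and 4: 0.5, 0.5, 1 and 2 mg (Table 3-1). Reduction rules: one dose level (3.5.2.2); same dose or 50% after Grade 3, 50% or stop after Grade 4 (Appendix 3).

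**Restart grade.** 3.5.2.2: Grade 2 or lower. Appendix 3: Grade 1 or lower, or baseline. The difference is one grade at every dose level. The baseline option does not close the gap for neuropathy: Protocol 1.6 says subjects with ongoing neuropathy above Grade 1 are excluded, and inclusion criterion 7 requires acute toxic effects of prior therapy to be Grade 1 or lower.

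**Resumed VCR dose after a Grade 3 VCR-related event.**

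| Level | Assigned VCR | 3.5.2.2 | Appendix 3 | Largest ratio |
|---|---|---|---|---|
| 4 | 2 mg | 1 mg | 2 mg, or 2 × 0.5 = 1 mg | 2/1 = 2 |
| 3 | 1 mg | 0.5 mg | 1 mg, or 1 × 0.5 = 0.5 mg | 1/0.5 = 2 |
| 2 | 0.5 mg | one level down is still 0.5 mg | 0.5 mg, or 0.5 × 0.5 = 0.25 mg | see below |
| 1 | 0.5 mg | no lower level; discretion after Sponsor discussion | 0.5 or 0.25 mg | see below |

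At Levels 3 and 4 one dose level equals a 50% cut, so the conflict there is a mandatory reduction against an optional one. At Level 2 the step down lowers only GS-9973, so 3.5.2.2 yields no VCR reduction unless 0.5 mg is treated as the lowest VCR level. At Level 1 it gives no dose.

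**Grade 4.** At Levels 3 and 4 the reduced doses agree (1 mg and 0.5 mg). Only the restart grade differs, and Appendix 3 also allows discontinuation.

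**Dexamethasone.** At Grade 3, 3.5.2.2 requires a hold where Appendix 3 says only to consider one. At Grade 4 both require a hold, but the restart grades differ (2 or lower against 1 or lower or baseline).

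**Precedence.** 3.5.2.1 points to Appendix 3 for GS-9973. 3.5.2.2 does not mention Appendix 3, and no other text ranks the two. The section heading cannot settle the matter, because both texts are about VCR.

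**The case against.** The strongest reply is that a careful site can comply with both texts. At Levels 3 and 4, waiting for Grade 1 and halving VCR satisfies each. 3.5.2.2 also sends sites to the product label for specific toxicity management. That stands, but it depends on a site noticing both texts, and waiting is not free under the 2-week removal rule. As an illustration, a subject who reaches Grade 2 on day 10 of a hold and Grade 1 on day 20 continues under 3.5.2.2 but would be removed if the site waited for Grade 1.

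Four stronger readings are tempting and should not be drawn.

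- **That GS-9973 has conflicting restart rules too.** The wording of 3.5.2.2 literally takes in every drug. But its heading and follow-up instructions cover only VCR and dexamethasone, and 3.5.2.1 gives GS-9973 its own rule: sites "will hold dosing of GS-9973 until the toxicity resolves to" Grade 1 or lower. The synopsis agrees. Counting the GS-9973 texts as further contradictions of 3.5.2.2 would inflate the conflict; this is a scope note only.
- **That the last sentence of 3.5.2.2 is another contradiction.** It says toxicities "must resolve to Grade 2 or to baseline levels before proceeding with the next cycle of treatment". That is a gate to the next cycle, separate from restarting a held drug. For GS-9973 it fits Appendix 3, which keeps the current dose at Grade 2 in the dermatological, hepatic and other-event rows.
- **That safety tables would depend on which text a site used.** SAP 7.1.6.1 combines reductions and interruptions in one summary by study drug. Both texts withhold VCR for a Grade 3 VCR event, so it enters the VCR summary whatever the restart grade or dose.
- **That escalation is affected.** No modification is allowed in Lead-in or Cycle 1, which is the DLT window.

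**Conclusion.** The conflict is real and minor. For VCR after a Grade 3 non-hematologic toxicity beyond Cycle 1, the protocol states two incompatible rules: they differ by one grade on restart and by up to 2-fold in resumed dose at Levels 3 and 4. For Grade 4 events at those levels only the restart grade differs. For dexamethasone the texts differ on whether a Grade 3 event requires a hold and on the Grade 4 restart grade.

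The reach is small. Dose escalation is complete (Protocol 3.3), expansion closed with no subjects enrolled (3.3.2), and maintenance under 3.3.3 requires at least a partial response. Only subjects still on treatment after Cycle 1 are exposed. The documents do not say how many there are or how often such toxicities occur, so no expected number can be given. The conclusion rests on the current text of 3.5.2.2, which gives Grade 2 in two sentences, and on the intact Grade 3 cell of the VCR table.

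**What to change.** State one VCR rule in both 3.5.2.2 and Appendix 3, taking the more cautious element of each:

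- After VCR-related non-hematologic toxicity of Grade 3 or greater, restart VCR only at Grade 1 or lower or baseline, reduced by one level: 1 mg from Level 4, 0.5 mg from Level 3.
- For subjects on 0.5 mg (Levels 1 and 2), resume at 0.25 mg or stop, after discussion with the Sponsor. Protocol 3.5.3 already uses a 50% cut at the lowest level for hematologic toxicity.
- Keep discontinuation as an option after Grade 4.
- When dexamethasone is held, use the Grade 1 or baseline threshold for restart.
- Limit 3.5.2.2 to toxicity attributed to VCR or dexamethasone, and say that GS-9973 follows 3.5.2.1 and Appendix 3.

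Simply adopting the Appendix 3 dose option is not advised. It would remove a mandatory VCR reduction and allow a full-dose restart after Grade 3 neuropathy, and the documents give no reason for that.

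The cost is a few sentences of protocol wording, or a clarification letter to sites with subjects still on treatment. It needs no extra subjects or procedures. The drawback is that some subjects will wait longer and may reach the more-than-2-week removal rule; the sponsor should accept that knowingly.

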Duration of Treatment:	Subjects may continue receiving GS-9973 until refractory disease at the end of induction, relapsed disease, start of new therapy, unacceptable toxicity, withdrawal of consent by subject, or withdrawal from study by investigator.
Diagnosis	Inclusion Criteria
and Main Eligibility Criteria:	Subjects must meet all of the following inclusion criteria to be eligible for participation in this study:
(see	1) ≥ 18 years of age
Protocol for Details)	2) Previously treated ALL including Philadelphia chromosome (BCR-Abl) positive ALL who meet all of the following criteria:
	a) Diagnosis of precursor B-cell ALL based on flow cytometry and histology
	b) Previously treated subjects with primary refractory disease OR after first or subsequent relapse
	c) Subjects with >10% lymphoblasts in bone marrow or extramedullary disease (EMD) that is radiographically measureable and amenable to imaging studies and repeat biopsies
	 d) Patients with Ph+ ALL must have failed treatment with at least one 2nd generation (eg. dasatanib) or 3rd generation (eg. ponatinib) tyrosine kinase inhibitor

- 3) Eastern Cooperative Oncology Group (ECOG) performance status ≤ 2
- 4) Adequate organ function defined by the screening laboratory value inclusion and absence of known cardiac dysfunction
- 5) Required screening laboratory data (within 7 days prior to administration of GS-9973) (Table 4-1)
- 6) Discontinuation of all therapy (including radiotherapy, chemotherapy, tyrosine-kinase inhibitors [TKIs], immunotherapy, or investigational therapy) for the treatment of cancer as follows:
 - a) At least 1 week or 5 half-lives (whichever is longer) from the last dose of prior anti-cancer therapy and the initiation of study therapy
 - b) Exceptions or modifications to the above are as follows: Medications that are typically part of a maintenance therapy for ALL, such as glucocorticoids or mercaptopurine, may be administered up to 3 days prior to the first dose, except vinca alkaloids which must be discontinued at least 14 days prior to the start of study treatment. TKIs are not permitted to be continued at screening (eg, Gleevec). Subjects may receive hydroxyurea or leukapheresis if indicated for rapidly rising white blood cell count
 - c) CNS prophylaxis should be dosed up at least one week prior to first dose of GS-9973
 - d) For biologics (eg, monoclonal antibodies), washout period of at least 4 weeks or 5 half-lives (whichever is shorter) since the last dose

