6.7. End of Study Treatment Assessments

Subjects will be removed from study treatment when any of the criteria listed in Section 6.8 apply.

The following procedures will be conducted when a subject goes off study treatment and prior to initiating a new regimen.

If the subject chooses not to continue participation on the study, the procedures listed below are to be conducted within 14 days of the last dose of study treatment or prior to initiating a new therapy.

- Review prior/concomitant medication
- Record any adverse events
- Performance status (ECOG)
- Modified physical exam including weight
- Vital signs; including blood pressure, respiratory rate, pulse, temperature, oxygen saturation level
- Laboratory assessments (Section 6.2.6.):
 - Chemistry
 - Hematology
 - Coagulation
 - Biomarker sampling
- Obtain bone marrow aspirate/biopsy samples for disease assessment and Biomarker testing
- CT scan or PET-CT of affected site/s for subjects with EMD only and without measureable BM involvement unless imaging was performed within 30 days of end of treatment (Patients with no BM involvement and only EMD will not require BM aspirate/biopsy)

6.7.1. **30-Day Follow-up**

After the last dose of study drug, subjects should be followed for any drug-related AEs and/or ongoing serious adverse events (SAEs) until those events have resolved or become stable, whichever occurs later. The site will contact the study subject regardless of AE/SAE status approximately 30 days after the subject's last dose of study drug to assess adverse events since the last study visit and review concomitant medications. Subject should be contacted by phone (or in person, if necessary) to assess the subject's condition and record any adverse events reported during the follow-up contact. Phone call or visit should be documented.

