6.8. Criteria for Discontinuation of Study Treatment

Study medication must be discontinued in the following instances:

- Intercurrent illness that would, in the judgment of the investigator, affect assessments of clinical status to a significant degree. Following resolution of intercurrent illness, the subject may resume study dosing at the discretion of the investigator
- Unacceptable toxicity, or toxicity that, in the judgment of the investigator, compromises the ability to continue study-specific procedures or is considered not to be in the subject's best interest
- The investigator, in consultation with the Gilead Medical Monitor or designee, may withdraw any subject from the study treatment, if, in the Investigator's opinion, it is not in the subject's best interest to continue
- Subject request to discontinue for any reason. Any subject has the right to withdraw from the study at any time
- Subject noncompliance with study treatment administration, study procedures, or study requirements should be withdrawn from study treatment in circumstances that increase risk or substantially compromise the interpretation of study results
- Any subject who becomes pregnant or begins breastfeeding should be withdrawn from study drug; refer to Appendix 5
- Discontinuation of the study at the request of GSI, a regulatory agency or an institutional review board or independent ethics committee (IRB/IEC)

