2.2. Final Analysis

Final study reporting is expected to occur after all subjects have discontinued the study.

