4. SUBJECT DISPOSITION

4.1. Subject Enrollment and Disposition

A summary of subject enrollment will be provided by dose level for each country and overall based on all enrolled subjects. The summary will present the number and percentage of subjects enrolled. For each column, the denominator for the percentage calculation will be the total number of subjects analyzed for that column.

A summary of subject disposition will be provided by dose level based on FAS. This summary will present the number and percentage of subjects in the following categories:

- ENTO discontinuation
 - Reasons of ENTO discontinuation
- VCR discontinuation
 - Reasons of VCR discontinuation
- Dexamethasone discontinuation
 - Reasons of dexamethasone discontinuation
- CNS prophylaxis discontinuation
 - Reasons of CNS prophylaxis discontinuation
- Included in the DLT analysis set
- Study discontinuation
 - Reasons of study discontinuation

The denominator for the percentage calculation will be the total number of subjects in FAS corresponding to that column.

A data listing of all enrolled subject enrollment to describe the site, subject number, date of first and last dose and dose level of ENTO, analysis set inclusion (FAS and DLT analysis sets), reasons for all study drugs' discontinuation, and reasons for study discontinuation will be provided.

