4.2.1. Duration of Exposure to Study Drugs

Total duration of exposure to study drugs will be defined as last dosing date minus first dosing date plus 1, regardless of any temporary interruptions in study drug administration, and will be expressed in weeks using up to 1 decimal place (eg, 4.5 weeks).

The duration of exposure to ENTO, VCR, dexamethasone, and CNS prophylaxis will be summarized respectively using descriptive statistics. Besides, the number and percentage of subjects exposed to each drug will be presented as follows:

- ENTO: at least 1 day, 14 days, 21 days, 28 days, and 2, 3, 6, 9 months, etc.
- VCR: Cycle 1, Cycle 2, Maintenance Cycle 1, Maintenance Cycle 2, etc.
- Dexamethasone: Cycle 1, Cycle 2, Maintenance Cycle 1, Maintenance Cycle 2, etc.
- CNS prophylaxis: Cycle 1, Cycle 2

The number and percentage of subjects who have dose modification and dose interruption will also be summarized.

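### Section 3.5.2.2 states its removal trigger for non-toxicity holds the wrong way round (up to 4 weeks instead of more than 4 weeks), and no other section supplies the limit

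*Protocol*

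**What the plan says.** The rule is one sentence in Protocol Section 3.5.2.2, with two conditions and one mandatory consequence. The first condition begins "If protocol therapy is withheld for more than 2 weeks for toxicity" and covers toxicity at least possibly related to protocol therapy. The second condition and the consequence read "or up to 4 weeks for any other reason, subjects will be removed from protocol".

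Three other places bear on when a subject stops treatment:

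- Section 6.7 points to a single list: "Subjects will be removed from study treatment when any of the criteria listed in Section 6.8 apply".
- Section 6.8 is that list. Its first item, intercurrent illness, adds: "Following resolution of intercurrent illness, the subject may resume study dosing at the discretion of the investigator".
- The synopsis entry on duration of treatment says "Subjects may continue receiving GS-9973 until refractory disease at the end of induction, relapsed disease, start of new therapy, unacceptable toxicity", then adds withdrawal of consent and withdrawal by the investigator.

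In the SAP, Section 4.2.1 states "The number and percentage of subjects who have dose modification and dose interruption will also be summarized". Section 4.1 tabulates, separately, "Reasons of ENTO discontinuation" and the same for the other study drugs.

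**The concern.** A removal trigger needs a floor: a hold longer than some limit leads to removal. The toxicity limb has one. The non-toxicity limb has a ceiling, which is how one describes a hold that is tolerated. With a mandatory consequence attached, it says the reverse of what a hold limit is for. Short holds end participation and long ones are left without a rule.

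What is at stake is whether a subject stays on treatment after a hold unrelated to toxicity. Section 9.1.9 makes the investigator responsible for following the protocol, and the opening of Section 6 requires deviations to be documented. A site that keeps a subject after a 10-day hold for illness therefore deviates from the text as written. A site that obeys the text ends treatment that the sponsor very probably meant to continue.

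**Working it through.** The plan gives no figure to reproduce. The check has three parts: what the sentence says for a hold of given length, whether other text supplies the limit, and where the difference could reach the analyses.

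**1. The rule by length of hold**

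Let d be the length of the hold in days.

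- Toxicity limb: removed if d > 14.
- Other reason, as written: removed if 1 ≤ d ≤ 28; nothing stated if d > 28.
- Other reason, as evidently intended: removed if d > 28.

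| d | Toxicity hold | Other reason, as written | Other reason, intended |
|---|---|---|---|
| 7 | stays | removed | stays |
| 14 | stays | removed | stays |
| 15 | removed | removed | stays |
| 28 | removed | removed | stays |
| 29 | removed | not covered | removed |

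The written and intended rules disagree for all 28 values from 1 to 28, and again from 29 on. For holds of 1 to 14 days the written rule is harsher on a subject held for a non-drug reason than on one held for drug toxicity. No sensible rule would aim for that.

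**2. Search for a correcting limit**

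- Section 6.8 and the synopsis list: no criterion based on length of hold.
- Section 3.5.2.1 and Appendix 3: drug is held until the event resolves to the stated grade (Appendix 3 also accepts return to baseline), with no maximum duration.
- Section 3.4: the 7 days is the gap allowed between Cycles 1 and 2, not a removal limit.
- Sections 3.5, 3.5.3.1 and 3.5.3.2: the 14-day figures are durations of cytopenia.
- Section 5.2.4: covers single late or missed doses only.
- SAP: does not restate a hold limit.

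Section 3.5.2.2 is therefore the only source of the 4-week figure. Set beside Section 6.8, the written rule forbids what that section permits: resuming after an illness that interrupted dosing for 28 days or less. The intended rule and Section 6.8 are compatible.

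**3. Where it could reach the analyses**

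*Exposure and disposition.* A 10-day non-toxicity hold is an interruption under SAP 4.2.1 if the intended rule is used, and a discontinuation with a reason under SAP 4.1 if the written rule is used.

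*DLT evaluability.* Section 3.3.1.1 requires 21 days of GS-9973 and more than 50% of planned VCR and dexamethasone within study days 1 to 35, unless treatment-related toxicity is the cause of the shortfall. Take a hypothetical illness that stops all drugs on study days 8 to 14, and assume the clause applies in Cycle 1.

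- Intended rule: GS-9973 on 35 − 7 = 28 days; VCR 3 of 4 doses = 75% (the study day 8 dose is missed); dexamethasone complete, since its courses fall on study days 15–18 and 29–32. The subject is evaluable.
- Written rule: removed after 7 days of GS-9973. The subject is not evaluable and may be replaced.

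*End of induction.* A subject removed during Cycle 2 may miss the Day 28 marrow. Section 8.5.1 counts a subject without sufficient assessment as a failure for overall remission. Section 6.7 does schedule a marrow when treatment stops, so the assessment is at risk but not necessarily lost.

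**The case against.** The strongest reply is that nobody would apply the literal text. The first limb gives the direction, the sentence itself gives the number, and the rest of the protocol assumes that short gaps are tolerated. Section 6.8 allows resumption after illness, Section 5.2.4 lets dosing continue after a missed dose, and both documents plan summaries of interruptions. On this view it is an editorial slip, and Section 6.8 is evidence of the intended meaning.

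Most of that stands. The intent is easy to infer, and the clash with Section 6.8 exists only under the literal reading, so it is not a second defect. What does not follow is that the text can be left alone. This is a mandatory rule on stopping treatment, it is the only statement of the limit, and as worded it is wrong.

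A second reply is that it is too late to matter: expansion was closed with no subjects enrolled, and the SAP covers Phase 1b only. That limits the value of an amendment. However, SAP Section 1 says current subjects continue to be treated or followed, and maintenance may run to 36 cycles, so the clause may still have been in force.

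Two stronger readings are tempting and neither is supported. A reader might infer that subjects were wrongly removed and the results distorted; the documents report no removal under this clause. A reader might equally infer that the DLT and response analyses cannot be touched; the routes shown in the working mean that cannot be asserted either.

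**Conclusion.** The non-toxicity limb is wrong as written, and the documents contain no other hold limit to correct it. That the sponsor meant more than 4 weeks is an inference from the parallel limb and from Section 6.8, though a safe one.

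The consequence is minor and operational. The 3+3 rules, the MTD definition, the sample size and the escalation probabilities do not depend on this clause. Its possible effects are on individual subjects: interruption versus discontinuation, DLT evaluability if the clause is applied in Cycle 1, and the end-of-induction assessment if it is applied in Cycle 2. How many subjects, if any, had a non-toxicity hold, and which rule sites followed, is not stated, so no numerical effect on any reported rate can be given.

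**What to change.** In Section 3.5.2.2, change the second limb to *more than 4 weeks for any other reason*. That matches the form of the toxicity limb, removes the conflict with Section 6.8 and covers holds beyond day 28. No analysis needs to change.

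The cost is one phrase at the next amendment. The SAP says "Final study reporting is expected to occur after all subjects have discontinued the study". If no subject remains on treatment, an amendment has no purpose, and one line in the study report saying which rule was applied to non-toxicity holds, and whether any subject was removed under it, is enough.
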